3. STUDY PROCEDURES

- Patients who are seen in clinic for rotator cuff pathology will undergo treatment for their rotator cuff based

on a shared decision-making process with the orthopedic surgeon, irrespective of this study. Once a treatment plan is in place, the patient will be introduced to this study and presented with the opportunity to participate. If the patient agrees, a formal consent process will take place in clinic and the patient will undergo initial, baseline testing of strength, range of motion, pain scores, and patient reported outcome scores.

Therefore, patients will be either in the nonoperative arm or the operative arm of this study. Within each arm, patients will be randomized via computer to be placed in either the blood flow restriction (BFR) cohort or the traditional (non-BFR cohort). Patients will prospectively undergo rotator cuff rehabilitation using BFR or conventional therapy by physical therapists with extensive experience in rotator cuff rehabilitation who will undergo training on use of BFR.

The nonoperative group will be given identical rehabilitation protocols, with the only difference being the use of a BFR cuff during rehabilitation for the BFR cohort. Similarly, the operative group will be given identical rehabilitation protocols, with the only difference being the use of a BFR cuff during rehabilitation for the BFR cohort.

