Throughout this protocol patients will have a pre-operative visit, an early 2 week post operative visit to check range of motion and wound healing, a six week visit to monitor range of motion and potentially clear for active ROM and sling discontinuation, and a three month visit prior to clearance to being return to more aggressive activity. Strength and range of motion will be recorded at each of these visits in order to assess the primary endpoint.

Outcomes:

Primary Outcome:

- Strength to be measured via dynamometer at each clinic visit

Secondary Outcomes:

- Range of motion via goniometer
- Pain via visual analogue scale (VAS) pain scale at each visit
- Patient reported outcomes scores at each visit
- Fatty infiltration and muscle atrophy measured via ultrasound and compared to pre-operative imaging

Plan to recruit patients starting in June 2020. Will enroll patients and collect data from June-2020 to May 2021. Manuscript writing and submission to occur in June 2021.

Data analysis: The primary endpoint of this study was a maximum repetition total work deficit of 15% between the BFR and control group as measured by dynamometer. This was based on previous data showing that a strength deficit of 15% represents a clinically significant difference that is not likely attributable to limb dominance. Work deficit was calculated in each group by comparing the operative leg with the nonoperative leg to obtain a deficit percent. A power analysis was performed before the study to assess the number of patients needed to detect a 15% total work deficit between the BFR and control groups. With a power of 80% (beta level $\frac{1}{4} 0.80$, alpha level $\frac{1}{4} 0.05$), a sample size of 34 (17 patients per group) was obtained. Data will be provided to and analyzed by trained statisticians to determine differences in primary and secondary outcomes.

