All continuous data will be analyzed using independent 2-group t tests and reported as means \pm standard deviations. Categorical data will be compared between the 2 groups using chi-square tests and reported as counts and percentages. A preliminary test to confirm the quality of variances will be conducted prior to utilizing the t test to confirm the appropriate statistical analysis. Nonparametric equivalents Wilcoxon rank-sum and Fisher exact tests will be used as needed for nonnormal distributions and low variable numbers, respectively. A multivariable regression analysis was performed to assess potential confounding demographic variables.

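### The primary endpoint is a side-to-side deficit, and the plan recognises that limb dominance affects such a measure, but nothing specified records or adjusts for whether the affected shoulder is the dominant one

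*Combined protocol and SAP*

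**What the plan says.** All of the relevant text is in section 3 (Study Procedures) of the combined protocol and SAP.

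- **Endpoint.** "The primary endpoint of this study was a maximum repetition total work deficit of 15% between the BFR and control group as measured by dynamometer". It is derived within each patient: "Work deficit was calculated in each group by comparing the operative leg with the nonoperative leg to obtain a deficit percent".
- **Reason for 15%.** The plan relies on prior data that "a strength deficit of 15% represents a clinically significant difference that is not likely attributable to limb dominance".
- **Sample size.** For 80% power at alpha 0.05, "a sample size of 34 (17 patients per group) was obtained". No SD is given.
- **Comparison.** "All continuous data will be analyzed using independent 2-group t tests and reported as means". The t test has no covariates.
- **Regression.** "A multivariable regression analysis was performed to assess potential confounding demographic variables". Neither its outcome nor its variables are named.
- **Randomisation and baseline.** Patients are randomised by computer within the operative and nonoperative arms, and no other stratification factor is stated. Baseline testing covers strength, range of motion, pain and patient-reported outcomes. No analysis is said to use the baseline strength value.

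Limb dominance appears only in the reason for the 15% figure.

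**The concern.** A side-to-side deficit uses the patient's other shoulder as the reference for normal. If the dominant side is naturally stronger, that reference is too low when the dominant shoulder is affected, so the deficit is understated. It is too high when the non-dominant shoulder is affected, so the deficit is overstated. Both kinds of patient are eligible.

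A 15% threshold can help to judge whether one person's deficit exceeds what dominance would produce. It removes nothing from a comparison of two group means, which is what the plan carries out. Dominance of the affected side is fixed before randomisation and plausibly shifts the outcome. Left out of the model, it adds to the residual spread. With 17 patients per group, an uneven split also moves the estimated BFR effect in a way that a reader could not check unless the item had been recorded.

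**Working it through.** **1. The plan's own figure.** Without an SD, the 17 per group cannot be reproduced, so I solved for the SD. A two-sided 0.05 t test with 17 per group, a difference of 15 points and 80% power implies an SD of about 15.1 (15.6 by the normal approximation). At SD 15, power is 80.7%. The sample size is attainable and not shown to be wrong. I use SD = 15 (variance 225) below.

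**2. Assumptions not in the documents.** The dominant side is stronger by s = 5% to 10% in health. The affected shoulder is at f = 75% of its own normal. The share of patients whose affected shoulder is dominant is p = 0.5 to 0.6 (up to 0.7 for imbalance).

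**3. Gap in mean deficit.**
- Dominant side affected: deficit = 1 - f(1 + s).
- Non-dominant side affected: deficit = 1 - f/(1 + s).

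| s | Dominant affected | Non-dominant affected | Gap |
|---|---|---|---|
| 5% | 1 - 0.75 x 1.05 = 21.3% | 1 - 0.75/1.05 = 28.6% | 7.3 points |
| 10% | 1 - 0.75 x 1.10 = 17.5% | 1 - 0.75/1.10 = 31.8% | 14.3 points |

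**4. Share of outcome variance** = gap² x p(1 - p)/225.
- Gap 7.3: 7.3² x 0.25/225 = 0.059, or about 6%. It is also about 6% at p = 0.6.
- Gap 14.3: 14.3² x 0.25/225 = 0.227, or about 23%. It is 22% at p = 0.6.

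**5. Power.** Shrinking the SD by the square root of (1 - share) suggests 83-89% after adjustment. That ignores what the covariate costs: one degree of freedom and its own chance imbalance. I therefore simulated the regression itself (17 v 17, total SD 15, true difference 15, p = 0.5 to 0.6).

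| Gap | Unadjusted t test | Adjusted for dominance |
|---|---|---|
| 0 (no dominance effect) | about 81% | 79-80% |
| 7.3 points | about 81% | 81-82% |
| 14.3 points | about 81% | 88% |

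With no true difference, the unadjusted test rejected in about 5% of runs whatever the gap.

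**6. Chance imbalance**, from two independent binomial counts out of 17.
- The groups differ by 3 or more patients with probability 0.39, 0.38 and 0.35 at p = 0.5, 0.6 and 0.7.
- They differ by 5 or more with probability 0.12, 0.11 and 0.09.
- A difference of 5 patients, such as 12 v 7, shifts the group difference by gap x 5/17. This is 7.3 x 5/17 = 2.1 points, or 14.3 x 5/17 = 4.2 points.
- The SD of the shift over all randomisations is gap x √(2p(1 - p)/17). At p = 0.5 this is 1.3 points (gap 7.3) or 2.5 points (gap 14.3).

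**7. If the planning SD left dominance out.** Steps 4 and 5 take the SD of 15 to include dominance variance. If the implied SD of 15.1 excludes it, the unadjusted test has power of about 79%, 76% and 71% at gaps of 5, 10 and 15 points (p = 0.6). It would then need 18, 19 and 21 per group.

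**The case against.** The strongest reply is that any unadjusted prognostic variable in a randomised trial behaves this way. Randomisation balances dominance in expectation, and the t test's standard error already includes its variance and chance imbalance. This stands. A reader might infer that the primary test is biased or invalid. The documents do not support that, and the simulation shows the nominal error rate.

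A reader might also infer that no analysis could take dominance into account. That is too strong. The multivariable regression lists no variables, so handedness could be among them. The baseline tests listed in section 3 include no demographics at all, so that list is not a full account of what is collected. What can be said is that nothing is specified. The regression is confined to demographic variables, and it is not stated to replace the t test.

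The 15% sentence does not give the size of a dominance effect in the shoulder. It says that 15% is unlikely to be due to dominance, and the following sentence refers to legs.

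The benefit is also modest. At the low end it is about one point of power, and the 12 v 7 split is a tail case: at p = 0.6, about 62% of randomisations (1 - 0.38) differ by two patients or fewer. Baseline strength is already tested, and adjusting for the baseline deficit would carry much of the fixed dominance effect. All of this stands and limits the weight of the point. It does not remove it, because no baseline adjustment is planned either.

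**Conclusion.** The point holds as a minor, inexpensive improvement in precision and interpretability. The plan recognises that dominance can produce a side-to-side difference, uses a side-to-side difference as its endpoint, and specifies nothing to handle it.

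Under the stated assumptions, dominance accounts for about 6-23% of outcome variance. Adjustment gains between almost nothing and about seven points of power. An imbalance of five or more patients, with a 9-12% chance, shifts the estimate by 2-4 points against a 15-point target.

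The size depends on inputs that the documents do not give: the SD, the dominance effect in the shoulder, the residual strength of the affected side and the share of dominant-side tears. Two further points are unsettled. It is unclear whether 34 is the whole trial or one treatment arm, which changes the imbalance probabilities. The outcomes list also gives the primary outcome simply as dynamometer strength, whereas the calculation here applies to the deficit.

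**What to change.** Record hand dominance and affected side at the baseline visit, and derive one variable: affected shoulder is the dominant one (yes/no). Make the primary analysis an ANCOVA of the percent deficit on treatment group, with the baseline deficit and this variable as pre-specified covariates. Strength is already tested at baseline. The plan should state that both shoulders are measured then, so that a baseline deficit can be calculated.

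The dominance term costs one question, one degree of freedom and a sentence in the analysis plan. If dominance has no effect, about one point of power is lost. Once the baseline deficit is in the model, much of the gain from the dominance term is already captured. How much depends on the correlation between baseline and follow-up deficits, which the documents do not give.

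### The powered primary endpoint is a leg-to-leg work deficit that does not fit a shoulder trial and cannot be formed for the nonoperative arm

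*Combined protocol and SAP*

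**What the plan says.** All of the relevant text is in section 3 (Study Procedures) of the combined protocol and SAP.

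- **Arms.** After a treatment decision made outside the study, "patients will be either in the nonoperative arm or the operative arm of this study". Allocation to BFR or control is then nested in the arms: "Within each arm, patients will be randomized via computer to be placed in either the blood flow restriction (BFR) cohort".
- **Listed primary outcome.** "Strength to be measured via dynamometer at each clinic visit". The visit description adds: "Strength and range of motion will be recorded at each of these visits in order to assess the primary endpoint". The visits are one before surgery, one two weeks after it, one at six weeks and one at three months.
- **Powered endpoint.** The Data analysis paragraph names a maximum repetition total work deficit of 15% and gives its only definition: "Work deficit was calculated in each group by comparing the operative leg with the nonoperative leg to obtain a deficit percent". It supports the 15% as a difference unlikely to be explained by limb dominance.
- **Sample size.** Patients were counted "to detect a 15% total work deficit between the BFR and control groups" with 80% power and alpha 0.05, and "a sample size of 34 (17 patients per group) was obtained". No SD, standardised effect or sidedness is given.
- **Test.** Continuous data are compared by independent two-group t tests.
- **Baseline.** Before treatment, "the patient will undergo initial, baseline testing of strength".

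**The concern.** The endpoint that carries the power calculation is written for a different limb and assumes that every patient has an operated side. Neither condition holds here. The joint is the shoulder, and one of the two arms has no surgery.

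Two things are at stake. First, the analyst has no written rule for computing the primary endpoint in nonoperative patients, and the Outcomes list does not supply one. Movement and primary visit are named in neither place, and the list and the Data analysis paragraph describe different quantities. Those choices could therefore be made after the data are seen. Second, the 80% power is attached to a quantity that is not defined for this trial's patients. A reader cannot tell whether 34 patients are enough for the shoulder endpoint that will actually be analysed.

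**Working it through.** **1. Can the deficit be formed?**

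| Element | Data analysis paragraph | Outcomes list | Needed in this trial |
|---|---|---|---|
| Limb | leg | not named | shoulder |
| Contrast | operative v nonoperative side, percent | none | one that exists in both arms |
| Metric | maximum repetition total work | strength | one metric |
| Movement | not named | not named | one |
| Primary visit | not named | every clinic visit | one |

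Replacing leg by shoulder repairs the first row for operative patients only. A nonoperative patient has no operative side, so the contrast in the second row still does not exist for that arm. The visits are also timed from surgery, and no separate schedule is given for nonoperative patients, so a common primary visit has no stated time origin.

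**2. Can 17 per group be reproduced?**

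Inputs from section 3: difference 15%, power 80%, alpha 0.05, 17 per group, t test. Assumptions: 15% means 15 percentage points between groups, and the test is two-sided. The SD is not given, so the plan's figure cannot be reproduced directly. It can only be solved backwards.

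For n per group, d = 15/SD, the noncentrality is d × √(n/2) and the degrees of freedom are 2n − 2. Power is the probability that a noncentral t exceeds the two-sided 5% critical value in absolute size.

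- n = 17: 80% power needs d = 0.991, so SD = 15/0.991 = 15.14.
- n = 16: 80% power needs d = 1.024, so SD = 15/1.024 = 14.65.

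So 17 is the smallest group size giving 80% only for an SD between about 14.65 and 15.14. The corresponding range is about 15.1 to 15.6 by the normal approximation and 16.7 to 17.2 for a one-sided t test.

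**3. How much depends on the missing SD?**

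Two-sided t test, 15-point difference, 32 degrees of freedom (critical value 2.037) at 17 v 17. All SDs are assumptions.

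| SD | d | Noncentrality, d × √8.5 | Power at 17 v 17 | n per group for 80% |
|---|---|---|---|---|
| 12 | 1.25 | 3.64 | 94.2% | 12 |
| 15 | 1.00 | 2.92 | 80.7% | 17 |
| 20 | 0.75 | 2.19 | 56.4% | 29 |
| 25 | 0.60 | 1.75 | 39.6% | 45 |

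**4. What do the two arms do to the power?**

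- Pooled analysis with a term for arm: degrees of freedom fall from 32 to 31. At SD 15, with the same effect and SD in both arms, power goes from 80.7% to 80.6%.
- 34 split evenly over the arms, each analysed alone: 34/4 = 8.5, so 8 or 9 per group. At SD 15, power is 46.1% with 8 per group and 51.3% with 9 per group.
- 34 in each arm: the trial total would be 2 × 34 = 68.

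The plan does not say which of these applies.

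**The case against.** The best reply is that leg is a slip, and that the Data analysis paragraph otherwise does its job. It names a metric, total work by dynamometer. It names a side-to-side contrast expressed as a percent, and it explains why 15% was chosen. Much of this stands: it would be wrong to say that metric and side are left wholly open. What remains is that the contrast does not exist for nonoperative patients, that the Outcomes list describes something else, and that movement and primary visit are missing from both.

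A reader might infer that the trial has no analysable primary outcome. The documents do not support that. Dynamometer strength is recorded at each visit and can be compared by t test; what cannot be formed as written is the deficit percent behind the power.

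A reader might also infer that 34 is too few. The documents do not support that either. An SD near 15 reproduces the figure, and the larger SDs above are assumptions without a source. A missing SD makes the number uncheckable, which is a supporting point and not a second error.

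Finally, 34 might be taken as the total over both arms. That reading is natural for a BFR-versus-control comparison, but the text leaves it open.

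**Conclusion.** The definition of the powered primary endpoint is wrong as written and must be corrected. It names the wrong limb, and it cannot be computed in the nonoperative arm even after that word is changed. This conclusion rests on the text alone and needs no assumption.

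The sample size is unverifiable. Its dependence on the unstated SD is steep: power at 17 v 17 runs from 94% to 40% over assumed SDs of 12 to 25. These figures assume that 15% is a 15-point difference between groups and that the test is two-sided. The plan justifies 15% as a within-patient limb difference and then uses it between groups, so that reading should also be confirmed.

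**What to change.** 1. Replace the leg definition with one shoulder endpoint computable in both arms. One option is the total work deficit of the affected against the unaffected shoulder. Another is affected-shoulder strength adjusted for the baseline strength already collected; this needs its own target difference, because the 15% is a side-to-side figure.
2. Make the Outcomes list state the same endpoint. Name one movement and one primary visit, with a time origin that applies to operative and nonoperative patients alike.
3. Include the operative/nonoperative arm, within which patients are randomised, as a term in the BFR-versus-control analysis.
4. State whether 34 (17 per group) covers both arms together or applies to each.
5. Restate the power for the corrected endpoint, with sidedness and either a sourced SD or a range of SDs. The SD should not be back-solved from the 80%.

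**Cost.** Items 1 to 5 need rewording and a recalculation. The side-to-side version also needs a brief dynamometer test of the opposite shoulder, which the plan does not describe. Either version needs confirmation of which nonoperative visit will be used. The arm term costs one degree of freedom, about 0.1 percentage point of power at SD 15. The restated power may be less favourable: if the SD were 20, the investigators would have to accept 56% or obtain 29 evaluable patients per group (2 × 29 = 58), before any allowance for withdrawals.

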10. WITHDRAWAL OF SUBJECTS

- Subjects will be withdrawn from the study if they are unable to tolerate the BFR therapy. Additionally, if they suffer from any complications of the therapy they will be withdrawn immediately. This will be facilitated by describing the reasons for withdrawal to the patient prior to initiating the study and ask patients and other providers to inform the investigators if there are any issues or concerns.

- Data collection on patients who were withdrawn will be terminated and data destroyed.
- Patients may withdraw from the study at any time for any reason without affecting the quality of their care

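### The 80% power applies to 34 analysable patients; the plan makes no allowance for losses, although its withdrawal rules remove patients and their data

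*Combined protocol and SAP*

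**What the plan says.** **Sample size.** Section 3 (Study Procedures, Data analysis) says: "A power analysis was performed before the study to assess the number of patients needed". The target is "to detect a 15% total work deficit between the BFR and control groups", with 80% power and alpha 0.05. The result is "a sample size of 34 (17 patients per group) was obtained". No SD, sidedness, loss rate, replacement rule or larger enrolment figure is given.

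**Analysis.** The same section says: "All continuous data will be analyzed using independent 2-group t tests". It describes no method for missing data.

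**Withdrawal.** Section 10 (Withdrawal of Subjects) gives three routes out of the study: inability to tolerate blood flow restriction (BFR), complications of the therapy, and the patient's own choice ("Patients may withdraw from the study at any time for any reason without affecting the quality of their care"). For all of them, "Data collection on patients who were withdrawn will be terminated and data destroyed".

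**Arms.** Section 3 randomises separately within a nonoperative and an operative arm. It does not say whether 34 covers both arms together or each one.

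**The concern.** A power calculation returns the number of patients who must contribute a primary measurement. Here that number appears alone, while section 10 ensures that a withdrawn patient contributes nothing, not even measurements already taken. If 34 patients are randomised and some leave, fewer than 34 are analysed, and the 80% in section 3 describes a larger dataset than the trial will have.

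What is at stake is how a null result is read. A non-significant comparison would be set against 80% power for 15 points, when the power available was lower and the difference the trial could reliably detect was larger.

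**Working it through.** **Inputs from the document:** difference 15 (read as 15 percentage points of work deficit), power 80%, alpha 0.05, 17 per group, independent t test.

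**Assumed, because not stated:** two-sided test; common SD; loss rates.

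**Formula.** With d = difference / SD and group sizes n1 and n2, the noncentrality is d × √(n1·n2/(n1+n2)) on n1+n2−2 degrees of freedom. Power is the probability that a noncentral t with these parameters exceeds the central 97.5% point; the other tail is negligible.

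**Step 1: the plan's own figure.** Without an SD, 17 per group cannot be reproduced directly, so I solved for the SD.
- Exactly 80% at 17 v 17 needs d = 0.991, so SD = 15 / 0.991 = 15.14.
- Exactly 80% at 16 v 16 needs d = 1.024, so SD = 15 / 1.024 = 14.65.
- Any SD from 14.65 to 15.14 therefore rounds up to 17 per group. SD 15 (d = 1.0) is a convenient value inside that range.

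At d = 1.0 and 17 v 17, the noncentrality is √(289/34) = 2.915, the critical value on 32 degrees of freedom is 2.037, and power is 80.7%. Seventeen per group is thus the bare t-test requirement, with only rounding to spare.

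**Step 2: fewer patients analysed, SD 15, true difference 15 points.** Detectable difference = 15 × the d that gives 80% power at those group sizes.

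| Analysed | Lost from 34 | Power | Detectable at 80% (points) |
|---|---|---|---|
| 17 v 17 | 0 | 80.7% | 14.9 |
| 17 v 16 | 1 | 79.4% | 15.1 |
| 16 v 16 | 2 | 78.1% | 15.4 |
| 17 v 14 | 3 | 76.4% | 15.7 |
| 16 v 15 | 3 | 76.7% | 15.6 |
| 15 v 15 | 4 (12%) | 75.3% | 15.9 |
| 14 v 14 | 6 (18%) | 72.1% | 16.5 |
| 14 v 13 | 7 (21%) | 70.4% | 16.8 |
| 13 v 13 | 8 (24%) | 68.7% | 17.2 |

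**Step 3: an illustrative 10–20% loss.**
- 34 × 0.9 = 30.6, so 30 or 31 remain: power 75.3–76.7%, detectable difference 15.6–15.9 points.
- 34 × 0.8 = 27.2, so 27 or 28 remain: power 70.4–72.1% (about 71% by interpolation at 27.2), detectable difference 16.5–16.8 points.

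Together this is about 71–77% power and a detectable difference of about 16–17 points.

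**Step 4: sensitivity to the back-solved SD.**
- SD 14.65: 82.5% at 17 v 17, 81.3% at 17 v 16, 80.0% at 16 v 16, 77.2% at 15 v 15.
- SD 15.14: 80.0% at 17 v 17, 78.7% at 17 v 16, 74.5% at 15 v 15.

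The slack is therefore between none and two patients. If the test was one-sided, 80% at 17 v 17 implies an SD of 17.2, and power falls similarly: 75.3% at 15 v 15 and 69.6% at 13 v 13.

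**The case against.** Several points on the other side are fair, and they limit what can be claimed.

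- **Number randomised.** The document never says that 34 will be enrolled. It says that the calculation gave 34, and it bounds recruitment by dates (June 2020 to May 2021). Treating 34 as the number randomised is an inference, though no other figure is offered.
- **No losses at all.** A reader might infer that the 80% holds only if nobody leaves. That is too strong. At the lower end of the compatible SD range two losses, one from each group, still leave 80.0%, and at SD 15 one loss leaves 79.4%.
- **Expected losses.** A reader might also infer that the plan expects losses. It permits withdrawal, in terms usual for consent, but forecasts no rate. Section 4 cites a very low complication rate for BFR tourniquets, and section 2 lists inability to tolerate BFR or to complete therapy among the exclusions. No loss percentage used here comes from the document.
- **Arithmetic.** Nor do the documents show that 17 per group is miscalculated. It reproduces under a plausible SD; what is missing is the SD and a statement of which patients the 80% refers to.
- **Size.** A 12% loss costs about 5 points of power and 1 point of detectable difference, and a null result should in any case be judged by its confidence interval.

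All of this stands. It does not remove the point: there is no allowance beyond rounding, and the destroyed data cannot be recovered for analysis. Because withdrawal for BFR intolerance can occur only in the BFR group, the same rule could also bias the comparison. That is a separate matter and is not sized here.

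**Conclusion.** The point holds in a limited form. The 80% belongs to 34 analysable patients, and the document does not say so. If 34 is the number randomised, power falls below 80% after about one or two losses, to about 75% with 30 analysed and 69% with 26. The detectable difference grows from about 14.9 points to 15.9 and 17.2.

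This rests on a two-sided 0.05 t test, an SD of about 15 that is back-solved rather than stated, a true difference of 15 points, and loss rates chosen for illustration. If 34 is meant per treatment arm, the same figures apply within each arm, and still no allowance is made. The effect is moderate and calls for an accurate statement of power, not a redesign.

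**What to change.** In section 3 (Data analysis), restate the sample size along these lines:

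*Thirty-four analysable patients (17 per group) [overall / in each treatment arm] give 80% power to detect a difference of 15 percentage points in work deficit, assuming an SD of [value used] and a two-sided 0.05 t test. If 34 are randomised and 10–20% have no primary measurement (an illustrative range), power is about 71–77% and the difference detectable with 80% power is about 16–17 points.*

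The last sentence assumes an SD near 15 and should be recalculated if the SD actually used differs. Report the number analysed in each group, and interpret the primary result, with its confidence interval, against that number.

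The cost is a change of wording and a less favourable stated power. No extra enrolment is required. If the sponsor would rather keep 80% after losses, randomising 34 / 0.9 = 37.8, so 38, would cover a 10% loss; 34 / 0.8 = 42.5, so 43 (44 in equal groups), would cover 20%.
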